We will be able to study important bio-behavioral factors in a concomitant manner that are specific to the central tenets of ingesting a hemp-extract that contains CBD and other minor cannabinoids. Biological factors to be studied include clinical signs of reduced symptomatology and functional limitations as well as quicker recovery to baseline that are indicative of anti-inflammatory and analgesic effects of CBD ingestion. Additional prior work by our group shows robust associations among pain intensity and measures of negative affect. Thus, we will also be able to study pain-related fear-avoidant and anxiety behaviors that are involved in the participants' perception of the threat or anticipation of a painful experience related to intense exercise and injury before, during and after undergoing our experimental injury model.

5. Specific Aims of Study:

Our overall objective is to generate preliminary data in humans on the effects of ingesting a hemp-extract investigational product that contains CBD for reducing pain-related anxiety and symptoms related to induced muscle injury. We aim to determine the efficacy of a controlled short-term trial of hemp-derived CBD ingestion for reducing symptomatic response and facilitating recovery following induced muscle injury. We will assess, in serial fashion, symptomatic response (both physical and psychological factors), functional limitations and recovery of the quadriceps muscle following induced injury in which selected doses of a hemp-derived CBD oil will be administered orally during a 15-day pre-injury consumption and post-injury recovery phase. We will evaluate these responses with an experimental repeated-measure design spanning pre-treatment, baseline measurement, injury induction, short-term sublingual administration of a hemp-derived CBD extract (or placebo) and recovery.

Aim 1: To determine time-related patterns of symptomatic and functional recovery in response to sublingual administration of either a low-dose or a high-dose CBD extract after muscle injury. Based on the purported anti-inflammatory, analgesic, and anxiolytic effects of CBD ingestion, we hypothesize that short-term sublingual administration of a hemp-derived CBD extract will limit the symptomatic response and functional limitations after induced muscle injury allowing for an expedient recovery to baseline conditions.

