Aim 2: To determine the impact of sublingual administration of a CBD extract on psychological factors known to influence pain intensity and duration. The investigation of psychological constructs will include evaluating the effects of sublingual administration of a CBD extract on pain-related anxiety, catastrophizing and fear pertaining to participants' views and perceptions toward engaging in strenuous physical exercise, sustaining a musculoskeletal injury and prolonged symptomatic and functional recovery. We hypothesize that the anxiolytic effects of sublingual administration of a CBD extract will diminish the threat and perceived physical stress of exercise-induced pain, physical harm, and prolonged symptomatic and functional recovery.

This exploratory study will provide preliminary data needed to support the hypotheses of a planned larger scale application. Preliminary data will help in better designing a future study aimed at identifying an efficacious dose range of hemp-derived CBD extract, as well as determining the cellular and molecular mechanisms that contribute to symptom resolution and recovery. Our findings may also be helpful for making future improvements for treating a broader range of inflammatory conditions that afflict the musculoskeletal system.

6. Research Plan:

Study Location & Design

The project will involve one study center located on the campus of the University of Florida. Data collection for the study will take place in the Sports Medicine & Human Performance Research Laboratory ([name]). The study protocol will be submitted to the UF Gainesville Health Science Center Institutional Review Board (IRB-01) located in the Gainesville Health Science Center ([name]).

The design will be a double-blind, randomized, vehicle-controlled, three-arm trial. Participants will be randomly assigned to either an active CBD dose group (n=15) or vehicle-control (placebo) group (n=15).. The effects of the active CBD dose groups will be compared to the vehicle-control. Subjects will be required to complete a 15-day study trial spanning a presupplement baseline visit, a controlled daily dosage regimen, pre-exercise baseline testing, eccentric exercise to induce muscle damage, and planned follow-up post-exercise data collection time points.

Study Population

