Study personnel will perform a follow-up phone call at 1 week after completion from the study for continued safety monitoring. Study personnel will refer to the checklist to determine if the participant has experienced or is experiencing any side effects or adverse events using the safety monitoring guidelines. If the participant reports experiencing any of the side effects/adverse events from the checklist the study physician will be consulted immediately for guidance and the participant's condition will be followed until full resolution.

Primary Outcome Measures: Self-report ratings of muscle soreness will be used to determine efficacy for duration of soreness and peak intensity of soreness. A muscle soreness inventory will be used to self-report the level of soreness. The muscle soreness inventory consists of rating soreness on a visual analog scale (VAS). A 10cm line is drawn with 0 (no soreness) on the left pole and 10 (extreme soreness) on the right pole. The inventory asks participants to rate their level of soreness by placing a slash on the line that best represents

their current level of soreness and soreness at its worst, best and average over the past 24 hours. The highest worst soreness intensity recorded during the recovery time will be recorded as the peak intensity of soreness. Measures of anxiety and fear of pain/soreness will also be recorded using a similar VAS. **Disability** will be measured using the Lower Extremity Functional Scale (LEFS).³⁷ The LEFS is a self-report questionnaire containing 20 items concerning an individual's ability to perform everyday tasks. The scale can be used to evaluate the functional impairment of a patient post-exercise of one or both lower extremities. Each item includes a 0-4 point hierarchical grading scale with 0 being "extreme difficulty or unable to perform activity" and 4 being "No difficulty". Subjects will rate their level of function for each of the 20 items for a total of 80 points. Each subject's score will be divided by 80 and recorded as a percentage value. LEFS scores will be recorded regularly until recovery and the highest score during this period will be recorded as peak lower extremity disability.

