Participants will be informed during the consenting period, both in writing on the consent form and verbally, that participants will likely experience soreness and stiffness within the exercised muscles after completing the exercise protocol. We postulate that participants will likely experience some level of heightened fear and anxiety (pain-related or other) in the 10-day wash-in phase of the investigational test article before they undergo the experimental exercise protocol and recovery phase. We feel this will be quantifiable on the self-reported psychological questionnaires that the participants will complete before and after the experimental protocol.

Data Management & Analysis

All information and data collected will be stored in locked filing cabinets or in computers with security passwords and accessed only by members of the research team. This process facilitates

data entry and collection, allows for participants to complete self-report questionnaires, and offers optimal security for collecting research-related information. The proposed Data Management will be housed within the Human Performance Laboratory and a secure webbased platform approved by UF (e.g. Redcap) will be used.

Outcome measures will be analyzed using a two-way ANOVA with repeated measures (between-group; within-time) or distribution free test (e.g Friedmans) as indicated by data distribution. Statistical significance will be set at p<0.05. If significant interactions occur, the Tukey post-hoc test will be used to reveal where the differences occur. We will calculate effect sizes and estimates of precision for all outcomes. All data analyses will be performed using SPSS® for Windows 16.0 (SPSS, Inc., Chicago, IL).

A **Data and Safety Monitoring Plan** will consist of two components: (1) overseeing participant safety and data monitoring, and (2) performance of monitoring. Since this project is viewed as low potential risk, all key personnel will perform all data and safety monitoring on an as needed basis.

7. Possible Benefits:

There is no known direct benefit from participating in this study. Study participants have the option of being paid for their time performing research related duties or they may choose to receive extra credit for a course they are currently taking and that may or may not be considered a benefit. There are no other obvious benefits to the study participant.

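### For soreness, LEFS and PCS, the plan does not say whether the group effect or the group-by-time interaction decides if CBD beats vehicle

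*Combined protocol and SAP*

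**What the plan says.** All of the following is in the Combined protocol and SAP.

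- **Section 6, Data Management & Analysis.** "Outcome measures will be analyzed using a two-way ANOVA with repeated measures (between-group; within-time", with a distribution-free test as the alternative. Then: "Statistical significance will be set at p<0.05". The only further rule is: "If significant interactions occur, the Tukey post-hoc test will be used to reveal where the differences occur".
- **Section 6, Study Location & Design.** "The effects of the active CBD dose groups will be compared to the vehicle-control". No test is named.
- **Section 5, Aim 1.** The aim is "To determine time-related patterns of symptomatic and functional recovery in response to sublingual administration". The hypothesis is that CBD "will limit the symptomatic response and functional limitations after induced muscle injury allowing for an expedient recovery to baseline conditions".
- **Section 6, Primary Outcome Measures.** "Self-report ratings of muscle soreness will be used to determine efficacy for duration of soreness and peak intensity of soreness". These two summaries are one value per person and stand beside the serial ratings.
- **Section 6, visit descriptions.** Soreness, LEFS and PCS are taken at Visits 1–6. MVIC and the stair test (TSCT) are taken at Visits 2–6. FPQ-9, PASS-20, PSQI and QST are taken at Visits 1, 2 and 6. Product is dispensed at the end of Visit 1 (Day 1), and the injury is induced at the end of Visit 2 (Day 11).

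**The concern.** The point concerns one serial outcome at a time, not the number of outcomes. The ANOVA table has two lines that involve arm, both read at 0.05. The Tukey rule says what to do after a significant interaction. It does not say what counts as CBD beating vehicle, or what follows if only the group line is significant. The Aim 1 hypothesis fits either line: a smaller response is a difference in level, and a faster return to baseline is a difference in pattern over time.

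The same data could therefore be read as positive or negative depending on the line chosen after the results are known. The results are meant to support a larger application, and its readers could not tell which test the efficacy statement rests on. Neither line isolates the level question either. Two of the six visits in the group F precede the injury, and the interaction is undirected and also responds to a Day 1 to Day 11 change.

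**Working it through.** **Inputs from the documents.** Two arms of 15; six visits, two before injury and four after; threshold 0.05. The plan gives no power figure, SD, correlation or effect size, so there is no stated figure to reproduce.

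**Assumptions.** Normal data; equal between-visit correlation of 0.3, 0.5 or 0.7; SDs either all 1 or with the two pre-injury SDs at 0.25. Effects are in post-injury SDs.

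**Step 1: the tests.** The group F has 1 and 28 df. The interaction has 6 − 1 = 5 and 28 × 5 = 140 df.

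**Step 2: false positives if either may be claimed.**
- Two independent tests: 1 − 0.95² = 9.75%.
- Simulated (40,000 trials per setting), uncorrected: 9.7–9.9% with equal SDs, 8.7–10.2% over all settings.
- Simulated with Greenhouse-Geisser: 6.7–8.8%; a repeat run gave 6.4–8.7%.
- If correlation decays with visit spacing (AR(1), 0.5–0.9): 11.1–13.7% uncorrected, 9.0–9.8% corrected. Part of the uncorrected excess is failure of sphericity. The corrected excess over 5% comes from having two chances.

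**Step 3: disagreement (exactly one of group F and corrected interaction significant).** With a flat 0.8 SD post-injury effect, or one of 0.8, 1.0, 0.7, 0.4 SD at 24, 48, 72, 96 h, the tests disagree in 15–67% of trials. The top of that range needs equal SDs before and after injury. With small pre-injury SDs it is 15–36%.

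**Step 4: dilution of the group F (flat 0.8 SD, correlation 0.5, equal SDs).**
- Six-visit difference: (2 × 0 + 4 × 0.8)/6 = 0.533.
- Variance of a person's six-visit mean: (1 + 5 × 0.5)/6 = 0.583, SD 0.764.
- Noncentrality: 0.533/(0.764 × √(2/15)) = 1.91. Power on 28 df is about 45%, as simulated.
- Visit 3–6 mean adjusted for Day 1: difference 0.8; variance (1 + 3 × 0.5)/4 − 0.5² = 0.625 − 0.25 = 0.375, SD 0.612. Noncentrality: 0.8/(0.612 × √(2/15)) = 3.58, power about 93%.

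Part of this gain comes from dropping the pre-injury visits and part from the baseline adjustment. With small pre-injury SDs the group F loses less: its power in this case is about 68%.

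**Step 5: power over all settings.**

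| Assumed effect | Group F | Interaction, corrected | Visit 3–6 mean adjusted for Day 1 |
|---|---|---|---|
| Flat, or peaking at 48 h | 31–81% | 57–96% | 85–97% |
| Late only (0, 0.2, 0.8, 1.0 SD at 24–96 h) | – | 66–98% | 55–68% |

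The contrast's simulated null rate is 4.9–5.1%.

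**The case against.** **The interaction is implied.** Aim 1 speaks of patterns over time, and the Tukey rule attaches to interactions only. This is the strongest reply, and the interaction is a defensible choice for the recovery half of the hypothesis. But a follow-up rule is not a success criterion, and nothing stops a significant group effect from being claimed alone.

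**The study is exploratory.** It claims no error-rate control and promises effect sizes and precision for every outcome. That limits the weight of the point. It does not remove it, because the protocol also aims to determine efficacy and sets a significance threshold.

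**The mean contrast can lose.** This stands. If CBD leaves the early response unchanged and only speeds late recovery, the interaction has more power (step 5). A reader might infer from the first row of that table that the contrast is better in every setting. The documents do not support that, because faster recovery is one of the two effects they hypothesise.

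**One template cannot serve all outcomes.** This stands. MVIC and TSCT have no Day 1 value, and FPQ-9, PASS-20, PSQI and QST have only Visit 6 after injury. The protocol also expects fear and anxiety to rise during the wash-in, so Day 11 matters for Aim 2.

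**Conclusion.** The concern holds for soreness, LEFS and PCS. Two arm-related tests share one threshold and neither is named as deciding. If either may be claimed, the per-outcome false-positive rate is about 9–10% uncorrected, or about 6–9% with Greenhouse-Geisser, under the equal-correlation settings. These figures rest on assumed correlations and SDs. That one outcome has two chances does not depend on them. The group F as written also dilutes a post-injury effect, by an amount that depends on pre-injury variability.

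Three stronger readings are tempting, and the documents do not support them:
- **That the two tests usually disagree.** The documents give no variances. People with current hip, leg or knee pain are excluded, so pre-injury soreness may vary little, and the lower disagreement rates are then the relevant ones.
- **That the stated soreness endpoints have two chances.** Peak and duration are single values per person with no time factor, so this problem does not touch them.
- **That the trial is invalid.** It is a preliminary study and the gap can be closed by wording. The sponsor should fix it, but it is not fatal.

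**What to change.** Add to Data Management & Analysis, before unblinding:

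1. **Soreness VAS, LEFS, PCS.** The deciding test of a reduced response is the CBD-minus-vehicle difference in the mean of Visits 3–6, adjusted for the Day 1 value, two-sided at 0.05 with a 95% CI. It is not conditional on a significant interaction. The group-by-time F and by-visit comparisons are supportive evidence on recovery pattern. The group F over all six visits does not carry a claim.
2. **Peak and duration endpoints.** Keep as stated under Primary Outcome Measures.
3. **MVIC and TSCT.** Mean of Visits 3–6 adjusted for Visit 2, stating that Visit 2 is an on-treatment, pre-injury value.
4. **FPQ-9, PASS-20, PSQI, QST.** Visit 6 adjusted for Visit 1, with Visit 2 reported for the wash-in hypothesis.

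The cost is a few sentences and no new data. The downside should be stated in the plan: if CBD only speeds late recovery, the mean contrast has less power than the interaction, and that effect would appear as supportive evidence and not as the deciding result.

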Visit 2 (Pre-exercise measurements and exercise protocol, Day 11)

Participants will be assessed actively (including vital signs) at each subsequent visit by study personnel using the side effects/adverse events checklist. Each participant will be read each side effect/adverse reaction from the checklist and instructed to self-report as yes (go) or no (no go). For participants who continue in the study, the following procedures will be performed: completion of psychological questionnaires (FPQ-9, PCS, PASS-20, PSQI, & LEFS), followed by tests of muscle soreness, quantitative sensory testing (QST), the timed stair climbing test (TSCT) and isometric strength measures to evaluate leg function. Participants will then undergo a standardized single bout of eccentric resistance exercise to the dominant quadriceps muscle. An isokinetic dynamometer (Biodex System 4 Pro, Biodex Medical Systems, Inc., Shirley, NY) will be used for the eccentric exercise protocol. Each participant will then perform five sets of twenty-five repetitions. Exercise will be performed using concentric (meaning shortening of muscles during contraction) and eccentric (lengthening of the muscle while still developing tension). The angular velocity will be set at 60°/sec for concentric and 90°/sec for eccentric actions. Participants will be given a three-minute rest period between sets. Each subject will receive \$15 for completing the test session.

Visit 3, 4, & 5 (Follow-up measurements @ 24, 48, & 72-hr post-exercise, Day 12, 13, & 14)
The following procedures will be performed: completion of psychological questionnaires (PCS & LEFS), followed by tests of muscle soreness and leg function testing (TSCT and isometric strength measures). Participants will receive \$5 for completing visits 3, 4 and 5.

Visit 6 (Follow-up measurements @ 96-hr post-exercise, Day 15)

The following procedures will be performed: completion of psychological questionnaires (FPQ-9, PCS, PASS-20, PSQI, & LEFS), followed by tests of muscle soreness, QST, and leg function testing (TSCT and isometric strength measures). At the end of the session each participant will be asked if they thought they were taking the active CBD product or placebo. Participants will receive \$10 for completing visit 6.

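### The only distribution-free test named, Friedman's, has no treatment-group term, so on that route the active-versus-vehicle comparison is not tested

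*Combined protocol and SAP*

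**What the plan says.** Section 6 of the combined protocol and SAP has a single analysis paragraph, under Data Management & Analysis, and it covers every outcome. The main route is a two-way repeated-measures ANOVA with group between participants and time within them. The alternative is "or distribution free test (e.g Friedmans) as indicated by data distribution". The significance level is 0.05, and the follow-up step is conditional: "If significant interactions occur, the Tukey post-hoc test will be used to reveal where the differences occur". The paragraph also promises estimation: "We will calculate effect sizes and estimates of precision for all outcomes".

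The comparison to be made is in Study Location & Design: "The effects of the active CBD dose groups will be compared to the vehicle-control". Two groups of 15 are described there.

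Primary Outcome Measures gives the efficacy measures: "Self-report ratings of muscle soreness will be used to determine efficacy for duration of soreness and peak intensity of soreness". Peak is derived explicitly: "The highest worst soreness intensity recorded during the recovery time will be recorded as the peak intensity of soreness". Duration is named but not derived. Disability is also reduced to one value: "LEFS scores will be recorded regularly until recovery and the highest score during this period will be recorded as" peak disability.

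**The concern.** A distribution-free substitute for a group-by-time ANOVA should keep the group question. Friedman's test keeps only the time question. The protocol itself expects soreness to rise after the exercise bout and to fade over 4-5 days, so a significant Friedman result is expected under vehicle as well as under CBD and says nothing about treatment. The Tukey step depends on a significant interaction, which Friedman cannot produce, so it is never reached on this route.

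The branch could well be used. People with current hip, leg or knee pain are excluded, so pre-exercise soreness is likely to sit near its floor and LEFS near its ceiling, with 15 per arm. That is an inference, since the documents give no soreness data. If it happens, the plan offers no between-arm test for these outcomes, and one would have to be chosen after the data are seen.

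**Working it through.** The plan states no effect size, SD or power, so there is no figure to reproduce. The check is structural, with simulations as illustration.

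**1. What Friedman uses.** With N participants, k visits, no ties, and R_j the sum over all participants of the within-participant rank of visit j:

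chi-square = 12 / [N k (k+1)] × Σ R_j² − 3 N (k+1), on k − 1 df.

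Arm labels do not appear. With N = 30 and the four post-injury visits, this is 0.02 × Σ R_j² − 450. Adding a constant to every score in one arm changes no within-participant rank, so Σ R_j² is unchanged. On one simulated data set without scale limits, Σ R_j² = 24,638 and the statistic was 0.02 × 24,638 − 450 = 42.76, both before and after 2 cm was added to one arm. In a separate five-time data set, lowering one arm by 1, 3 or 10 points left it at 83.36. An arm difference that varies over time can alter the pooled ranks, but the statistic cannot separate it from the common time course.

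**2. Degrees of freedom, 15 per arm.**

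| Term | Formula | k = 5 | k = 1 |
|---|---|---|---|
| Friedman | k − 1 | 4 | 0 |
| ANOVA time | k − 1 | 4 | 0 |
| ANOVA group-by-time | (2 − 1)(k − 1) | 4 | 0 |
| ANOVA within-participant error | (30 − 2)(k − 1) | 112 | 0 |
| ANOVA group | 1 and 30 − 2 | 1, 28 | 1, 28 |

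With one value per participant Friedman does not exist. The ANOVA keeps its group term on 1 and 28 df, which is the two-sample t-test.

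**3. Illustrative rejection rates (all inputs assumed).** Settings: post-injury means 4, 5, 3.5 and 2 cm, SD 1.5 or 2.5, within-person correlation 0.3 or 0.7, scores limited to 0-10, 1,000 trials per setting.
- Friedman, four post-injury visits: 0.987-1.000 with no effect; 0.988-1.000 with a 2 cm reduction.
- Rank-sum on peak soreness: 0.044-0.057 with no effect; 0.57-0.98 with a 2 cm reduction (t-test 0.61-0.98).

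A separate run of 2,000 trials used between- and within-participant SDs of 1.2 and 1.0 and a 1.5-point group shift. With a flat time course, Friedman rejected in 5.5% of trials without and 5.0% with the shift. With a soreness time course it rejected in 100% either way.

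**4. Which contrast a replacement can use.** From the visit descriptions:

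| Outcome | Visit 1 (Day 1, untreated) | Visit 2 (Day 11, pre-exercise) | Visits 3-5 | Visit 6 |
|---|---|---|---|---|
| Soreness, LEFS, PCS | yes | yes | yes | yes |
| FPQ-9, PASS-20, PSQI, QST | yes | yes | no | yes |
| Stair climb, isometric strength | no | yes | yes | yes |

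Visit 2 measures "tests of muscle soreness, quantitative sensory testing (QST), the timed stair climbing test (TSCT) and isometric strength measures to evaluate leg function", but after ten days of dosing, so it is not an untreated baseline. Take an equal 1 SD effect at Visits 2 and 6, with SD 1 and correlation 0.7 (assumed). The expected arm difference in Visit 6 minus Visit 2 is 1 − 1 = 0, so that contrast rejects at the 0.05 level whatever the effect (5.2% simulated). For the mean of Visits 2 and 6 minus Visit 1, the difference is 1 and the variance is (1 + 1 + 1.4)/4 + 1 − 1.4 = 0.45. The standardised difference is 1/√0.45 = 1.49 (97% simulated). Visit 6 alone gave 74%.

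**The case against.** The best defence is that the plan does not bind itself to Friedman. It is offered as an example, on a conditional branch, in a study described as exploratory, and effect sizes with precision are promised for every outcome. The ANOVA route suits the serial scores. Nothing in the documents says that a Friedman result would be read as a CBD effect. All of this stands, and it limits the weight of the point. It does not supply a test: no alternative that compares arms is named, and no estimator is given for the one-value measures. Running Friedman separately in each arm does not help, because comparing two within-arm p-values is not a test between arms.

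A reader might go further and infer that peak and duration of soreness have no usable test on either route. The documents do not support that. On the parametric route the named ANOVA reduces, for one value per participant, to its group term, which is an ordinary two-group comparison. The wording there is loose, but it has one obvious reading. Nor do the documents say that duration is one value per participant. That is its natural reading, whereas peak soreness and peak disability are explicitly single values.

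**Conclusion.** Wrong as written, within the distribution-free branch only. For serial outcomes, the one test named there answers whether scores change over time, not whether active differs from vehicle. For peak soreness and peak disability, and for duration on its natural reading, that test cannot be run. This follows from the form of the test and needs no assumed data.

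The rejection and power figures do rest on assumed means, SDs, correlations and effects, so they illustrate the fault and do not measure harm. The duration results also depend on what counts as recovered. Taking duration as the time to the first visit at or below the threshold, rank-sum power was 0.50-0.94 for 1 cm, 0.44-0.85 for 0 cm and 0.62-0.95 for the participant's own Visit 2 level. The exploratory status lowers the consequence. The correction is still worth making, because the data are meant to support the hypotheses and design of a larger study.

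**What to change.** In Data Management & Analysis, remove Friedman as the between-group fallback. It may stay as a within-arm description of the time course. Then state:

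1. **Peak and duration of soreness.** Wilcoxon rank-sum test between arms, with a two-sample t-test for peak on the parametric route. For duration, define recovery from the return to baseline named in the Aim 1 hypothesis, saying which visit is baseline. Give participants still sore at 96 h the shared top rank.
2. **Serial outcomes.** Rank-sum or permutation test between arms on per-participant summaries.
   - Soreness, LEFS, PCS, FPQ-9, PASS-20, PSQI and QST: change from the untreated Visit 1 value as the group contrast, naming the later visits that enter it.
   - Outcomes taken at Visits 2 to 6: also the injury response, as the mean of Visits 3 to 6 minus Visit 2.
   - Stair climb and isometric strength: the post-injury mean and its change from Visit 2, noting that Visit 2 is already on treatment.
   - Psychological and QST outcomes: Visit 6 minus Visit 2 must not be the sole contrast, because it cancels an effect already present after wash-in, which Aim 2 is meant to detect.
3. **Choice of route.** State before unblinding which outcomes take the distribution-free route.

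Peak disability gets the same rank-sum test once a separate matter is reconciled: LEFS items score 4 for no difficulty, so the highest total is best function, not greatest disability.

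The cost is analysis wording, the recovery definition and a simple rule for missed visits, with no new visits or data. A permutation test may need code outside the named package and must follow the allocation scheme actually used. If the data are normal, the rank-sum test loses a little power: at most 0.04 against the t-test for peak in the settings run.

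### Three unranked primary outcomes, and every other outcome, are each judged at p<0.05 with no lead outcome or correction across outcomes, giving about 8–14% familywise error on the primaries alone

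*Combined protocol and SAP*

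**What the plan says.** Section 6, Primary Outcome Measures, opens with two outcomes tied directly to efficacy: "Self-report ratings of muscle soreness will be used to determine efficacy for duration of soreness and peak intensity of soreness". Disability on the LEFS follows as a third. None is ranked above the others. The same heading also covers four soreness ratings per visit, "current level of soreness and soreness at its worst, best and average over the past 24 hours", and adds: "Measures of anxiety and fear of pain/soreness will also be recorded using a similar VAS". Peak intensity is fixed as the highest of the worst-soreness ratings over recovery. No rating or cut-off is fixed for duration.

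The secondary measures that follow number twelve: mechanical pain threshold, temporal summation, pressure pain threshold, conditioned pain modulation, isometric strength, stair-climb time, exertion and movement pain, FPQ-9, PCS, PASS-20 and PSQI.

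Section 6, Data Management & Analysis, treats all of these alike: "Outcome measures will be analyzed using a two-way ANOVA with repeated measures (between-group; within-time"), or a distribution-free alternative. The threshold is "Statistical significance will be set at p<0.05". The only multiplicity step is "If significant interactions occur, the Tukey post-hoc test will be used to reveal where the differences occur". The same paragraph promises effect sizes and precision for all outcomes.

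On purpose, the opening summary and the end of Section 5 call the study exploratory and preparatory to a larger one. The opening summary and Section 5 also state an aim of determining efficacy.

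**The concern.** When several outcomes share top rank and each has its own 5% test, a nominally significant result on any one can be presented as evidence of efficacy, and which one leads can be settled after the data are seen. Tukey does not help, because it adjusts comparisons within one outcome after a significant interaction. The findings are meant to support a larger application, so a chance result could shape the hypotheses and endpoint of that trial. The plan never says that its p-values are descriptive.

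**Working it through.** The plan gives no familywise error rate, power or sample-size calculation, so there is no figure of its own to reproduce.

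**Inputs**
- Per-test level 0.05 (Data Management & Analysis). Sidedness is not stated; two-sided is assumed, because an ANOVA F test has no direction.
- Three primary outcomes and twelve secondary outcomes (Section 6), so 3 + 12 = 15, with one treatment test each.
- 15 participants per arm (Section 6, Study Location & Design).
- Correlations between outcomes are not given. A range from 0 to 0.9 is assumed.

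**Chance of at least one p<0.05 with no true effect**

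For k independent tests this is 1 − 0.95^k:
- k = 3: 1 − 0.95³ = 14.3%
- k = 15: 1 − 0.95¹⁵ = 53.7%

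For correlated outcomes, k normal test statistics with common correlation ρ were simulated (400,000 draws), counting draws in which any exceeded 1.96 in absolute value:

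| Correlation ρ | 3 primaries | 15 outcomes |
|---|---|---|
| 0 | 14.3% | 53.7% |
| 0.5 | 12.6% | 36.2% |
| 0.8 | 9.8% | 20.2% |
| 0.9 | 8.3% | 14.4% |

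**Two variants for the primaries, assuming independence**
- LEFS is recorded serially. If both its group effect and its group-by-time interaction count as treatment tests, there are four tests: 1 − 0.95⁴ = 18.5%.
- If only results favouring CBD count, each test carries 0.025: 1 − 0.975³ = 7.3%.

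**Cost of control at 15 per arm** (normal approximation, 80% power)

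Detectable standardised difference = (z for the level + 0.842) × √(2/15), where √(2/15) = 0.365:
- level 0.05: (1.960 + 0.842) × 0.365 = 1.02 SD
- level 0.05/3 = 0.0167: (2.394 + 0.842) × 0.365 = 1.18 SD

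**LEFS definition.** Each item runs from 0 for extreme difficulty to 4 for none, so a high total means good function. The protocol nevertheless takes the highest score as peak disability, which picks each participant's best visit.

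**The case against.** The strongest reply is that this is a 15-per-arm study, labelled exploratory, that promises effect sizes and precision throughout. Strict familywise control in such a study is partly a matter of preference. That lowers the severity. It does not remove the point, because the same document speaks of determining efficacy, applies a significance threshold to every outcome, and ties the soreness ratings to efficacy in its definition of the primary outcomes.

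The reply also limits the size of the claim. Four stronger readings are tempting, and the documents do not support them:

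- A reader might double all three primaries, one test for group and one for interaction, and reach 1 − 0.95⁶ = 26.5%. Peak soreness and duration are one value per participant, so they have no time factor and no interaction. Only LEFS could supply a second test, and the protocol reduces LEFS to a single peak as well.
- A reader might take 54% as the error rate of the trial's efficacy claim. That figure assumes 15 independent outcomes and gives a lone secondary result the weight of a primary one. The protocol does separate primary from secondary, and soreness, disability, strength and stair-climb pain after the same injury are unlikely to be independent.
- A reader might infer that the choice among VAS soreness items is fully open. It is not for peak intensity, which is tied to the worst rating; it is open for duration. Nor does the plan say that each VAS item will be tested separately.
- A reader might treat the two-sided figures as the chance of a false claim of benefit. They also count results in which CBD looks worse than placebo.

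**Conclusion.** The concern holds at minor to moderate severity. Followed as written, the plan gives about 8–14% familywise error on the three primaries: up to about 18.5% if both LEFS tests count, and about 7% if the outcomes are independent and only results favouring CBD count. Over all 15 outcomes the range is 14–54%, with the top of it an independence bound and not an expected value. These figures rest on two-sided tests, one per outcome except where stated, and on assumed equal correlations, since the documents supply none. The inflation on the primaries is therefore roughly two- to threefold in most scenarios; a description such as far above 5% suits only the full set of outcomes.

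**What to change.** Before the blind is broken, amend the outcome and analysis paragraphs of Section 6 as follows.

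1. Name peak worst soreness, which the protocol already defines, as the single primary outcome at two-sided 0.05, compared between groups as one value per participant.
2. Correct peak LEFS disability to the lowest LEFS score, and state the VAS item and cut-off that define duration of soreness.
3. Test LEFS disability and then duration in that fixed order, each only if the preceding test is significant. Holm over the three is an acceptable alternative.
4. Report the secondary outcomes, including the Aim 2 questionnaires, as effect sizes with 95% confidence intervals labelled exploratory, and state that a lone p<0.05 among them is not an efficacy claim.

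The edit is a few sentences and changes no visit, sample size or treatment. It has real costs. Under the fixed order, a miss on peak soreness stops formal testing of the other two, at a sample size where 80% power needs about a 1.02 SD difference. Holm avoids that stop, but the smallest p-value must clear 0.0167, at which level the detectable difference is about 1.18 SD. Aim 2 has its own hypothesis and becomes descriptive, which fits the stated exploratory purpose.
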